9.2 Planned number of subjects

A statistical objective of the trial will be a prove of a non-inferior therapeutic efficacy and safety of the study drug Angal S comparing to the drug ANTI-ANGIN® FORMULA in the treatment of acute infectious and inflammatory diseases of the pharynx. Justification of a non-inferiority margin is based on the results of a placebo-controlled trial of pastilles with chlorhexidine and lidocaine conducted by [Kris De Ceulaer. A summary of a clinical trial proves that chlorhexidine/lidocaine lozenges are effective and safe. 11-8-2015].

This trial demonstrated absence of a sore throat (a TSS subscale) 3 days after the therapy initiation, on Day 4, in 37.5% patients in the trial arm and 63.1% patients in the placebo arm.

Table 2. Answers distribution results regarding questions on a sore throat at baseline and Day 4

	Baselii	ne visit	Ι)4
N	Product N=106	Placebo N=103	Product N=106	Placebo N=103
Sore throat				
Unknown	0	0	2 (N=104)	0
Absent	0 (0%)	0 (0%)	65 (62.5%)	38 (36.9%)
Mild	3 (2.8%)	3 (2.9%)	27 (26.0%)	45 (43.7%)
Moderate	77 (72.6%)	75 (72.8%)	11 (10.6%)	19 (18.4%)
Severe	26 (24.5%)	25 (24.3%)	1 (1.0%)	1 (1.0%)
p	1.0000		0.0	0016

Therefore, a lower limit of CI boundary may be calculated for the difference in sore throat presence after 3 days of therapy, taking into account 104 participants and 103 patients.

In view of the considered nosology and absence of significant factors requiring a conservative approach for determination of the

non-inferiority margin, for this purpose we can use a two-sided CI 90%. To calculate a two-sided CI 90%, a method described by Newcombe, Robert G. was used "Interval Estimation for the Difference Between Independent Proportions: Comparison of Eleven Methods," Statistics in Medicine, 17, 873-890 (1998). CI 90% will amount to 14.56–36.66%, i.e., the lower limit will correspond to one-sided CI 95%. Therefore, a margin of 14.5% is considered to be justified.

NCSS 8.0 Two Proportions Report

Dataset Untitled

Zero Adjustment Method: None

Note: Exact tests and c.i.'s were not run because total count > 50 (specified under 'Reports' tab).

Table Section

				N1	N2	M1	M2	N
A	В	\mathbf{C}	D	(A+C)	(B+D)	(A+B)	(C+D)	(N1+N2)
65	39	38	65	103	104	104	103	207

Confidence Intervals of Difference (P1-P2)

Interval	Estimated	Confidence	Confidence
Method	Value	Limit	Limit
Chi-Square (Pearson)	0.2561	0.1456	0.3666

(The calculation results are presented in the language of the original source, i.e., from NCSS 8 statistical program).

- This is a non-inferiority trial; therefore, a non-inferiority margin for the primary endpoint should be justified and amount to not more than 14.5%.
- An expected rate of positive response to therapy (absence of a sore throat as an efficacy measure) in a comparator drug arm is 63%.
- An expected rate of positive response to therapy (absence of a sore throat as an efficacy measure) in a study drug arm is 65% (chosen within the tested hypothesis and based on the sample size and expected positive response).
- A one-sided type I error (α) = 2.5 % (0.025)
- A type II error (β) = 20 % (0.2), which corresponds to 80% power.
- Expected discontinuation from the trial will amount to 10% during the treatment.

The tested hypotheses are worded as follows:

Null hypothesis (H0): difference in the primary 1. endpoint achievement Angal incidence while using S, the study drug, and ANTI-ANGIN® FORMULA, the original drug, for treatment of acute

infectious and inflammatory pharyngeal diseases will exceed 14.5% in favor of ANTI-ANGIN $^{\circledR}$ FORMULA

$$H_0: p_1 - p_2 \le -0.145$$

2. Alternative hypothesis (Ha): difference in the primary endpoint achievement incidence while using Angal S, the study drug, and ANTI-ANGIN® FORMULA, the original drug, for treatment of acute infectious and inflammatory pharyngeal diseases will not exceed 14.5% in favor of ANTI-ANGIN® FORMULA

$$H_A: p_1 - p_2 > -0.145$$

Where p₁ and p₂ is the primary endpoint achievement incidence while using the study drug Angal and the original drug ANTI-ANGIN® FORMULA, respectively.

To calculate a sample size in every group, one can use a formula presented by Chow S, Shao J, Wang H. 2008. Sample Size Calculations in Clinical Research. 2nd Ed. Chapman & Hall/CRC Biostatistics Series. page 90:

$$n = (p_1 \times (1 - p_2) + p_2 \times (1 - p_2)) \times \left(\frac{z_{1-\alpha} + z_{1-\beta}}{p_1 - p_2 - \delta}\right)^2$$

where:

n = Size of one group;

z = Normal distribution function at the set levels of α and β:

 δ = Non-inferiority margin;

 p_1 = Expected proportion in Angal group;

[figure not shown]
p₂ = Expected proportion in ANTI-ANGIN® FORMULA group.

Substituting the above data into this formula, we obtain a minimal number of patients in every group without account for withdrawal: 128 patient completed the trial (total 256 patients).

In view of the expected discontinuation from the trial during the therapy of 10%, not less than 280 patients are required for randomization (140 patients in each group).

The calculation results by the above formula were also checked using nQuery, a validated program (see below), and considered to be identical.

9.3 Applicable significance level

All statistical analyses in this trial will be conducted at 95% significance level (a threshold p value for confirmation of statistical significance is below 0.05), except for the primary endpoint where an onesided statistical criterion will be used with 97.5% significance level (a threshold p value is below 0.025). The two-sided statistical criteria will be used for all other parameters.

For the primary endpoint evaluation, 90% CI will be calculated for the proportions difference with further evaluation of its lower boundary limit.

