	- A rate of positive response to therapy (absence of a sore throat as an efficacy measure) in a comparator drug arm is 63%.
	- A rate of positive response to the therapy (absence of a sore throat as an efficacy measure) in a study drug arm is 65% (chosen within the tested hypothesis and based on the sample size and expected positive response).
	- Power = 80%
	- A non-inferiority margin is 14.5
	- Significance level: 97.5%
	- Randomization in 1:1 ratio (study drug: comparator drug).
	A number of patients required at 80% power and 2.5% one-sided significance level to prove the hypothesis of the study drug efficacy not more than 14.5% inferior to that of the comparator drug (determined by absence of a sore throat after 3 days of therapy) is 128 patients in every arm.
Interim analysis	An interim analysis may be conducted after receipt of efficacy data for Angal S and ANTI-ANGIN® FORMULA, spray, after 3 days of therapy, on Day 4, for at least 100 patients in every arm. During the interim analysis, demographic

and history data, as well as

	the available data on efficacy and safety of Angal S and ANTI-ANGIN $^{\otimes}$ FORMULA will be analyzed.
Blinding, randomization	This trial will be open, without blinding.
	The patients will be included by randomization in 1:1 ratio using envelopes at the trial site.

2. Trial rationale and a drug clinical trials program

Trial rationale

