This trial has been designed and conducted to evaluate non-inferiority of the therapeutic efficacy and safety of the study drug Angal S, topical spray [menthol] containing 0.5 mg of lidocaine hydrochloride and 2 mg of chlorhexidine digluconate per ml (Sandoz d.d., Slovenia), when compared to ANTI-ANGIN® FORMULA, topical metered spray giving 0.12 mg of tetracaine hydrochloride and 0.24 mg of chlorhexidine bigluconate per dose (OOO Valeant, Russia) in the treatment of patients with uncomplicated acute infectious and inflammatory diseases of the pharynx accompanied by a sore throat. The objective of this Phase III trial is to demonstrate the non-inferior therapeutic efficacy of the study drug as compared to the reference product.

This Statistical Analysis Plan was developed in accordance with the following documents:

- Guidelines for examination of medicinal products, Vol. 1. Federal State Budgetary Institution Scientific Center for Expert Evaluation of Medicinal Products under the Ministry of Health of the Russian Federation (eds. A.N. Mironov). Moscow: Grif and K, 2013.
- ICH harmonized tripartite guideline. Statistical principles for clinical trials (E9). Current Step 4 version dated 5 February 1998.
- GCP rules of the Eurasian Economic Union (a draft).

The objective of this Statistical Analysis Plan is more detailed, compared to Section 9 of the trial protocol, description of the main principles of the protocol-based statistical analysis, description of the primary and secondary endpoints analysis methods, as well as other data obtained during the trial.

This Plan stipulates for consistence of the scheduled and conducted statistical analysis to the trial protocol, including definition of the analysis data sets, transformations and calculations for the endpoints, observations quantity needed, etc. No changes in this Statistical Analysis Plan compared to the trial protocol are envisaged.

2. Trial endpoints

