3.10 Significance level

All statistical analyses in this trial will be conducted at 95% significance level (a threshold p value for confirmation of statistical significance is below 0.05), except for the primary endpoint where a one-sided statistical criterion will be used with 95% significance level (a threshold p value is below 0.05). The two-sided statistical criteria will be used for all other parameters.

For the primary endpoint evaluation, 90% CI will be calculated for the proportions difference with further evaluation of its lower boundary limit.

4 Analysis plan

For non-inferiority confirmation, a two-sided 90% CI will be calculated for the proportion difference of the primary efficacy parameters (no pain after 3 days of therapy on Day 4 according to TSS) with further evaluation of its lower boundary limit.

A non-inferiority conclusion will be made relating to the primary parameter only which will confirm the claimed efficacy. Secondary variables (including secondary efficacy and safety parameters) will be used for the research interest. Correction for multiple comparisons is not envisaged due to the trial arms number.

Descriptive statistics will include data for all randomized patients. Descriptive statistics parameters to be calculated for the quantitative variables are listed below:

- Quantity of observations (n);
- Arithmetic mean (M);
- Standard deviation (SD);
- 95% confidence interval for the mean (95% CI);
- Minimal value (min.);
- Maximal value (max.);
- Median (Me);
- Interquartile range (IQR).

For the variables presented as qualitative and serial parameters, the absolute (n) and relative (%) incidences will be calculated for every category, as well as 95% CI (unless otherwise specified).

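### The protocol sets the primary test at one-sided 2.5% and sizes the trial for it, but the 90% confidence interval rule and the SAP apply one-sided 5%, twice the stated false-positive rate.

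*Protocol*

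**What the plan says.** Three places in the protocol set the primary error rate at one-sided 2.5%:

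- Synopsis, statistical analysis: the sample size is computed "at 80% power and 2.5% one-sided significance level".
- Section 9.2: "A one-sided type I error (α) = 2.5 % (0.025").
- Section 9.3: the primary endpoint is the exception to the general level, "where an onesided statistical criterion will be used with 97.5% significance level (a threshold p value is below 0.025").

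The decision rule is set at another level. Section 9.1.2 confirms non-inferiority from a two-sided 90% confidence interval for the difference in proportions, by Newcombe's method. Section 9.3 repeats this directly after the 0.025 threshold: "For the primary endpoint evaluation, 90% CI will be calculated for the proportions difference with further evaluation of its lower boundary limit".

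The SAP keeps the 90% interval (3.10, 4, 4.1.2 and Figure 2) and changes the threshold: "where a one-sided statistical criterion will be used with 95% significance level (a threshold p value is below 0.05"). Its introduction states: "No changes in this Statistical Analysis Plan compared to the trial protocol are envisaged".

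**The concern.** The lower limit of a two-sided 90% interval is a one-sided 5% test. The protocol says so itself: in 9.2 it equates the lower 90% limit with a one-sided 95% limit. Section 9.3 therefore names two different error rates for one hypothesis. The SAP settles the conflict in favour of the looser rate and does not list this as a change, although Protocol 9.6 requires deviations from the statistical plan to be described and justified.

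SAP section 4 rests the non-inferiority conclusion on the primary parameter alone. If its error rate is ambiguous, so is the trial's conclusion: a result falling between the two limits could be reported as success under one sentence and failure under another.

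**Working it through.** **Inputs.** Rates 65% (study drug, p1) and 63% (comparator, p2), margin 14.5 points, power 80%, 128 evaluable and 140 randomised per arm, 10% loss (all Protocol 9.2). Newcombe interval (Protocol 9.1.2, SAP 4.1.2). With 10% loss, 140 × 0.9 = 126 per arm.

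**Step 1: which level does the sample size reflect?** With the usual unpooled variance,

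n = [p1(1 − p1) + p2(1 − p2)] × (z₁₋α + z₁₋β)² / (p1 − p2 + 0.145)²

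The variance term is 0.65 × 0.35 + 0.63 × 0.37 = 0.4606, and the denominator is 0.165² = 0.027225.

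- One-sided 2.5%: 0.4606 × (1.960 + 0.842)² / 0.027225 = 132.8, so 133 per arm.
- One-sided 5%: 0.4606 × (1.645 + 0.842)² / 0.027225 = 104.6, so 105 per arm.

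The plan's 128 is not reproduced exactly at either level. It is 5 short of the 2.5% figure and 23 above the 5% figure. Other variance choices at 2.5% give 132 to 138 (the formula as printed gives 137). The figure belongs to the 2.5% design.

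**Step 2: false-positive rate of each rule.** Newcombe's lower limit is

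L = d − √[(p̂1 − l1)² + (u2 − p̂2)²]

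where d = p̂1 − p̂2, and l1 and u2 are the Wilson lower limit for the study drug and upper limit for the comparator. Non-inferiority is declared if L > −0.145. Summing the binomial probabilities of all outcomes that pass, with true rates at the margin (48.5% against 63%):

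| n per arm | 90% interval | 95% interval |
|---|---|---|
| 126 | 5.1% | 3.0% |
| 128 | 4.9% | 2.8% |
| 140 | 4.9% | 2.8% |

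**Step 3: power at 65% against 63%.** Normal approximation, Φ(0.165/√(0.4606/n) − z₁₋α):

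| n per arm | One-sided 5% | One-sided 2.5% |
|---|---|---|
| 126 | 86.1% | 77.9% |
| 128 | 86.6% | 78.5% |
| 140 | 89.1% | 82.0% |

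Exact power of the Newcombe rules at n = 128 is 87.4% (90% interval) and 79.2% (95% interval). Any result that passes at 95% also passes at 90%, so at the planning rates the two rules disagree in 87.4 − 79.2 = 8.2% of trials.

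**Step 4: a result on which they disagree.** Take 128 per arm with 81 comparator responders (63.3%) and 76 study-drug responders (59.4%), so d = −0.0391.

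- 90%: l1 = 0.5211, u2 = 0.6995. L = −0.0391 − √(0.0726² + 0.0667²) = −0.138. Passes.
- 95%: l1 = 0.5071, u2 = 0.7113. L = −0.0391 − √(0.0866² + 0.0785²) = −0.156. Fails.

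With 77 responders the limits are −0.130 (passes) and −0.148 (fails).

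**The case against.** **The 90% interval may be deliberate.** It appears in every decision statement of both documents, and Protocol 9.1 leaves the full analysis to the SAP. One-sided 5% applied openly throughout would also be consistent. But the only rationale given for 90% (synopsis and 9.2, no factors calling for a conservative approach) concerns deriving the margin from the earlier lozenge trial. Nothing justifies 5% for this trial's test, and the sample size points to 2.5%.

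**The p-value threshold is not the same test as the interval.** This stands. The named test is a one-sided Fisher exact test, which as described tests equality and not the −14.5% null. It follows that p < 0.025 does not guard the non-inferiority claim. The interval alone does, and it runs at 5%.

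**A 95% interval does not give exactly 2.5%.** Also true: the Newcombe rule attains 2.8% to 3.0% here. Two further defects would remain: the optional interim look without correction (SAP 3.7), and the wording of the decision rule, which asks for a limit of 14.5% or lower where the hypotheses need a lower limit above −14.5%. These are separate points and do not remove the contradiction.

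**Power would fall just short of 80%.** At one-sided 2.5%, 128 per arm gives 78.5% by the approximation, and 126 gives 77.9%. That shortfall comes from the sample-size calculation and is hidden by the 90% interval.

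**Conclusion.** The concern holds. The protocol states one-sided 2.5% three times and decides at one-sided 5%. The SAP adopts 5% without declaring the change. The nominal error rate doubles exactly (0.05/0.025 = 2). In attained terms, the operative rule runs at 4.9% against the stated 2.5%, and against 2.8% for the matching 95% interval, a ratio of 4.9/2.8 = 1.75.

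These figures assume a comparator rate of 63%, equal arms, a pass defined as a lower limit above −14.5%, and no interim look. With comparator rates of 55% to 70% and 128 per arm, the 90% rule stays at 4.9% to 5.3% and the 95% rule at 2.6% to 2.9%. This must be fixed before analysis, because the documents support two different verdicts on the same data.

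**What to change.** State one level everywhere. To match the level used for the sample size:

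- Protocol 9.1.2 and 9.3, and SAP 3.10, 4, 4.1.2 and Figure 2: replace the two-sided 90% interval with a two-sided 95% interval.
- SAP 3.10: replace the one-sided threshold of 0.05 with 0.025, and tie it to the interval or to a test of the −14.5% null.

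If the sponsor prefers one-sided 5%, it should say so in the synopsis, 9.2 and 9.3, justify it for this trial's test, redo the sample-size statement at that level, and record the change as Protocol 9.6 requires.

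The first option changes wording only and needs no added patients, although Protocol 11.2 treats changes to statistical methods as significant amendments needing approval. The price is power: by the approximation, 78.5% instead of 86.6% at 128 per arm, and 82.0% instead of 89.1% at 140. Guaranteeing 80% after 10% loss would be a separate decision, needing 133/0.9 = 147.8, so 148 randomised per arm in place of 140.

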9.4 Trial termination criteria

The trial may be terminated under conditions described in Section 4.6 of this protocol.

9.5 Accounting for missed, unanalyzable, and questionable data

During the monitoring visits to the trial sites, the clinical trial specialists (monitors) authorized by the Sponsor will analyze eCRFs for the data completeness. In the case of absence of data on CRFs and availability of relevant information in the primary documentation, questions for investigators and regulations to address inconsistencies will be formulated. At the database check, the expert in statistics authorized by the Sponsor, and the data control and processing managers will analyze the trial results for questionable, missed, and unanalyzable data, which might be the basis for the questions for investigators. If possible, the investigators will eliminate the errors identified in CRFs and inform the Principal Investigator and authorized representatives of the Sponsor hereof. In case the identified data errors cannot be eliminated after the completion of the patients participation in the trial, the analysis of the resulting parameter sensitivity to questionable data will be conducted in the statistical analysis.

Information about the missed, questionable, and unanalyzable data will be summarized in the final clinical trial report.

The main analysis for the primary endpoint will be conducted without replacement for the missed, questionable, or unanalyzable data. An additional analysis will be conducted with the data replacement (last observation carried forward); in this case, the last known TSS score will be carried to all subsequent control points.

All other data will be analyzed based on actually available information only, without data replacement.

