4.2.4.6 Visit of premature discontinuation of the trial

Visit 2 procedures will be applied for the visit of premature discontinuation.

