5.3 Exclusion criteria

5.3.1 Terms and conditions for the subjects' exclusion from the trial

The subjects may be excluded from the trial on their own free will at any moment, without giving any reason, as well as upon decision of the Investigator or Sponsor in cases when continuation of the participation may inflict harm to the patient's health and/or life. In addition, the patient must be excluded in the cases listed below:

- 1. Negative course of the disease with signs of the secondary bacterial infection (including body temperature increase above 37.5 °C).
- 2. The Ethics Committee, regulatory authorities, or Sponsor terminate the trial or participation of the specific trial site for any reason.
- 3. The Investigator's decision to withdraw the patient from the trial in the interests of the patient.
- 4. Withdrawal of the informed consent (unwillingness of the patient to continue his/her participation in the trial).
- 5. Serious deviation from the trial protocol.
- 6. Individual intolerance of the study drugs.
- 7. Clinically significant adverse event or serious adverse event.
- 8. Patient's non-compliance.
- 9. False inclusion (e.g., the patient was included in breach of the inclusion/non-inclusion criteria).
- 10. The patient complies with the non-inclusion criteria during the trial.
- 11. The patient receives or requires an additional therapy which might influence the trial results or patient's safety (see *Prohibited concomitant therapy* section).

12. Other conditions or events which, in the Investigator's opinion, require the patient's exclusion from the trial.

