9.7 Selection of subjects for analysis

The following data sets will be used for analysis:

• The intention-to-treat (ITT) population: all randomized subjects who received at least one dose of the study drug/placebo and have completed at least one visit aimed at evaluation of the efficacy parameters (i.e., at least all the procedures of Visit 1).

According to the ICH E9 requirements, the ITT population will be considered to be a population for statistical analysis in the equivalence trials (including non-inferiority trials).

- The per protocol (PP) population: all randomized subjects who completed participation in the trial in accordance with the protocol (have completed the prescribed period of treatment and follow-up without significant deviations from the protocol).
- The safety population (safety): All randomized subjects who received at least one dose of the trial/reference drug and have completed at least one visit to the evaluation of the parameters of safety (i.e., at least all the procedures of Visit 1). As distinct from ITT population, the safety population will be analyzed depending on actually received treatment (not only prescribed) (in case of difference between the prescribed and received therapies).

Protocol No. TE_004_ANG_LOZ

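### Patients excluded before Day 4 for outcome-related reasons are not classed as non-responders, so the main primary analysis can lose treatment failures unevenly between arms

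*Protocol*

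**What the plan says.** The primary endpoint is the proportion without sore throat on the TSS at Visit 2, Day 4 (Protocol 4.1.1.1 and 7.2).

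- **Missing data.** Protocol 9.5 states: "The main analysis for the primary endpoint will be conducted without replacement for the missed, questionable, or unanalyzable data". It adds: "An additional analysis will be conducted with the data replacement (last observation carried forward"). SAP 3.6 repeats both statements.
- **Exclusion.** Protocol 5.3.1 introduces its list with "In addition, the patient must be excluded in the cases listed below". The list includes "Negative course of the disease with signs of the secondary bacterial infection", intolerance of the study drugs, a clinically significant or serious adverse event, and "The patient receives or requires an additional therapy which might influence the trial results or patient's safety". It also includes grounds with no necessary link to outcome, such as consent withdrawal, false inclusion and termination of a site. Excluded patients are not replaced (5.3.3).
- **ITT.** Protocol 9.7 and SAP 3.3 require one dose and that patients "have completed at least one visit aimed at evaluation of the efficacy parameters (i.e., at least all the procedures of Visit 1"). No Day 4 score is needed.
- **PP.** Patients must have completed treatment and follow-up according to the protocol (9.7).
- **Scores at withdrawal.** Protocol 4.2.4.6 says: "Visit 2 procedures will be applied for the visit of premature discontinuation". Table 1 lists the TSS at Visit 2, and unscheduled visits include it (4.2.4.5).

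**The concern.** A patient who is dosed and then excluded on Day 2 or 3 for one of the outcome-related reasons is an ITT member with no Day 4 result. No section says that this patient counts as still having a sore throat. None says whether a TSS taken at withdrawal may stand in for Day 4, and the form in Appendix 2 has no row for an early-withdrawal score. Without replacement, the natural reading is that the patient drops out of both numerator and denominator.

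The ITT analysis then becomes an available-case analysis, with missingness partly caused by the outcome being measured. PP offers no check, because it removes the same patients. SAP section 4 rests the non-inferiority conclusion on this one endpoint. The trial is open-label, and the Investigator both scores the endpoint and takes part in withdrawal decisions, so unequal withdrawal between arms is plausible.

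**Working it through.** **Inputs from the documents.** 140 randomised per arm, margin 14.5 points, comparator response 63%, and expected discontinuation 10%, which is 14 per arm (Protocol 9.2). The interval is Newcombe's for a difference of proportions (9.1.2). Results are given for both the 95% and the 90% interval, because Protocol 9.3 uses a one-sided threshold of 0.025 with a 90% interval, and SAP 3.10 uses 0.05 with a 90% interval.

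**Assumptions.** True rates among all randomised patients lie on the margin: 63% − 14.5 = 48.5% for Angal S against 63%. Every missing patient is a treatment failure. The numbers missing, k₁ (Angal S) and k₂ (comparator), are varied because the documents give no split by arm. The interval is taken as the version built from Wilson score limits.

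**Formulas.** Available-case rates are q₁ = 0.485 × 140 / (140 − k₁) and q₂ = 0.63 × 140 / (140 − k₂). The lower limit is d − √[(p₁ − l₁)² + (u₂ − p₂)²], where l₁ and u₂ are Wilson limits. False non-inferiority is the exact binomial probability that this limit lies above −14.5 points.

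**Starting point.** The plan gives no figure for the effect of missing data. With failures counted, the calculation gives 2.8% (95% interval) and 4.9% (90% interval), close to the nominal 2.5% and 5%. This holds whatever the split.

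| Failures missing, Angal S / comparator | Available-case rates | Difference | False non-inferiority, 95% CI | 90% CI |
|---|---|---|---|---|
| Failures counted | 48.5% / 63.0% | −14.5 | 2.8% | 4.9% |
| 3 / 0 | 49.6% / 63.0% | −13.4 | 3.9% | 7.5% |
| 14 / 7 | 53.9% / 66.3% | −12.4 | 5.6% | 10.1% |
| 14 / 0 | 53.9% / 63.0% | −9.1 | 14.9% | 23.3% |
| 14 / 14 | 53.9% / 70.0% | −16.1 | 1.4% | 2.8% |
| 7 / 14 | 51.1% / 70.0% | −18.9 | 0.4% | 0.8% |

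For 14/7, for example, q₁ = 67.9/126 = 53.9% and q₂ = 88.2/133 = 66.3%. The 3/0 row scales the only Day 4 missing-data figure in the documents, 2 of 106 against 0 of 103 in the lozenge trial (Protocol 9.2, Table 2): 2/106 × 140 ≈ 3.

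**One data set, two conclusions.** Take 80 and 88 pain-free patients of 140, with 14 and 7 failures missing.

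- Available cases: 80/126 = 63.5% against 88/133 = 66.2%. The lower limit is −12.3 (90%) or −14.1 (95%), so non-inferiority is shown.
- Failures counted: 80/140 = 57.1% against 88/140 = 62.9%. The lower limit is −15.2 (90%) or −16.9 (95%), so it is not shown.

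**The case against.** Several points on the other side stand.

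- **Mandatory exclusion is narrower than worsening.** A reader might infer that every worsening patient must be excluded. In 5.3.1 the ground is a negative course with signs of secondary bacterial infection. The synopsis leaves early discontinuation for worsening to the Investigator's decision and says patients may be excluded. A patient whose throat simply still hurts can stay and be scored as a failure on Day 4.
- **Not all missingness is failure.** The 5.3.1 list also has administrative grounds. Treating every missing patient as a failure, as the table does, is the extreme case.
- **Omission is not stated outright.** No denominator is given, and a withdrawal TSS may exist. This leaves an ambiguity to settle. It does not answer the concern, because no rule brings that score into the main analysis, and patients who refuse the visit are only telephoned (5.3.1.1).
- **Carrying the last score forward would tend to show the problem.** Entry requires throat pain, so a patient with only a baseline or worsening score is carried forward as not pain-free. But that analysis is only additional, and the decision rule in 9.1.2 gives it no role.
- **Counting every missing patient as a failure is not a safe remedy.** Suppose loss is unrelated to outcome, with true rates still on the margin and 7 Angal S and 14 comparator patients lost. Failure imputation gives 0.485 × 133/140 = 46.1% against 0.63 × 126/140 = 56.7%, a difference of −10.6 points. False non-inferiority is then 9.5% (95%) or 14.5% (90%), against 2.6% or 5.0% for available cases. This is why the fix must depend on the reason for withdrawal.

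**Conclusion.** The gap is real and should be closed before the data are analysed. As written, the plan can drop outcome-related exclusions from its only confirmatory comparison, and neither PP nor the additional analysis corrects this.

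The size is conditional. With all missing patients failures, and more of them missing on Angal S, false non-inferiority ranges from 3.9% (3/0) to 14.9% (14/0) with the 95% interval, and from 7.5% to 23.3% with the 90% interval. The reference values are 2.8% and 4.9%.

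A reader might go further and infer that the plan is biased towards non-inferiority. The documents do not support that. They give no discontinuation rates by arm, and equal loss or heavier loss on the comparator makes the plan conservative under the same assumptions.

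**What to change.** In Protocol 9.5 and SAP 3.6:

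1. In the main ITT analysis, count as sore throat present every dosed patient excluded before the Day 4 assessment for worsening, intolerance, an adverse event, or additional or prohibited therapy, whether or not a withdrawal TSS exists.
2. For patients missing Day 4 for other reasons, such as administrative reasons or consent withdrawal unrelated to outcome, keep available-case handling in the main analysis and state the denominator.
3. Report as sensitivity analyses: failure imputation for all missing patients, last observation carried forward, and complete cases. Tabulate missing counts and reasons by arm.
4. Reconcile the permissive wording on exclusion for worsening in the synopsis with the mandatory wording in 5.3.1.

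The change is to wording, and no new data are needed beyond recorded withdrawal reasons. Response rates become slightly lower. If completers respond at 65% and 63% and 10% per arm are outcome-related exclusions, the rates become 0.9 × 65 = 58.5% and 0.9 × 63 = 56.7%. Power with 140 per arm is then 80.2% (95% interval) or 86.9% (90% interval), against 78.9% or 86.5% for 126 available cases per arm, so power is not lost. The main burden is that withdrawal reasons must be classified in an open-label trial. The rules for this should be written down and the classification documented before analysis starts.
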